APPENDIX B. RESPONSIBILITIES OF THE INVESTIGATOR

Protocol M23-515: A Randomized, Double-blind, Placebo-controlled, Dose-finding Study to Evaluate the Safety, Efficacy, Pharmacokinetics, and Pharmacodynamics of ABBV-552 in Participants with Mild Alzheimer's Disease

Protocol Date: 13 December 2023

Clinical research studies sponsored by AbbVie are subject to the ICH GCP and local laws and regulations and guidelines governing the study at the site location. In signing the Investigator Agreement, the investigator is agreeing to the following:

- 1. Conducting the study in accordance with ICH GCP, the applicable regulatory requirements, current protocol and operations manual, and making changes to a protocol only after notifying AbbVie and the appropriate IRB/IEC, except when necessary to protect the participant from immediate harm.
- 2. Personally conducting or supervising the described investigation(s).
- 3. Informing all participants, or persons used as controls, that the drugs are being used for investigational purposes and complying with the requirements relating to informed consent and ethics committees (e.g., IEC or IRB) review and approval of the protocol and its amendments.
- 4. Reporting complaints that occur in the course of the investigation(s) to AbbVie.
- 5. Reading the information in the Investigator's Brochure/safety material provided, including the instructions for use and the potential risks and side effects of the investigational product(s).
- 6. Informing all associates, colleagues, and employees assisting in the conduct of the study about their obligations in meeting the above commitments.
- 7. Maintaining adequate and accurate records of the conduct of the study, making those records available for inspection by representatives of AbbVie and/or the appropriate regulatory agency, and retaining all study-related documents until notification from AbbVie.
- 8. Maintaining records demonstrating that an ethics committee reviewed and approved the initial clinical protocol and all of its amendments.
- 9. Reporting promptly (within one [1] calendar day to AbbVie, the ethics committees/IRBs [as required] and other appropriate individuals [e.g., coordinating investigator, institution director]):
 - All changes in the research activity and all unanticipated problems involving risks to human participants or others

APPENDIX D. ACTIVITY SCHEDULE

The following table shows the required activities during the study. The individual activities are described in detail in the Operations Manual (Appendix F).

Study Activities Table

Activity	Screening/Visit 1	Screening/Visit 2	Baseline/Day 1 Visit 3	Day 3 /Visit 4 (Telephone Visit)	Week 1 /Visit 5	Week 2 Visit 6	Week 4/Visit 7 (Telephone Visit)	Week 6 /Visit 8	Week 8/Visit 9 (Telephone Visit)	Week 10 /Visit 10 (Telephone Visit)	Week 12/Visit 11 (Premature Discontinuation)	30-Day Follow Up Visit	Unscheduled Visit
Week Relative to Study Drug Start			0	0	1	2	4	6	8	10	12	16	
Day Relative to Study Drug Start			1	3	8	15	29	43	57	71	85	115	
Study Visit Window (days)				±1	±2	±2	±з	±з	±з	±з	±3	±з	
☐ INTERVIEWS & QUESTIO	NNA	AIRES	6										
Informed consent	V												
Eligibility criteria	V												
Medical/surgical history	V												
Alcohol and nicotine use	V												
Adverse event assessment	V	✓	*	✓	✓	✓	✓	✓	✓	*	✓	*	✓
Prior/concomitant therapy	✓	✓	*	✓	✓	✓	✓	✓	✓	*	✓	*	✓
Assess study drug compliance				✓	✓	✓	✓	✓	✓	*	✓		
Assess Altoida DNS performance compliance				1	*	*	*	*	*	*	1		
IMAGING	4												
MRI	V										✓		~
CLINICAL OUTCOMES A	SSE	SSMI	ENTS										
ADAS-Cog 14	V	1	*					✓			✓		✓
C-SSRS	V		✓		✓	✓		✓			✓	*	✓
CDR	V										✓		✓
MMSE	*										>		✓
Cogstate Computerized Battery (CBB and ISLT)	~	*	*		✓	*		✓			1		✓
Altoida DNS (clinic only)	✓	>											>
Altoida DNS (once daily, clinic or home)			✓	✓	✓	✓	✓	✓	✓	✓	✓		
Neuropsychiatric Inventory (NPI)			✓								*		*

Activity	Screening/Visit 1	Screening/Visit 2	Baseline/Day 1 Visit 3	Day 3 /Visit 4 (Telephone Visit)	Week 1 /Visit 5	Week 2 Visit 6	Week 4/Visit 7 (Telephone Visit)	Week 6 /Visit 8	Week 8/Visit 9 (Telephone Visit)	Week 10 /Visit 10 (Telephone Visit)	Week 12/Visit 11 (Premature Discontinuation)	30-Day Follow Up Visit	Unscheduled Visit
Week Relative to Study Drug Start			0	0	1	2	4	6	8	10	12	16	
Day Relative to Study Drug Start			1	3	8	15	29	43	57	71	85	115	
Study Visit Window (days)				±1	±2	±2	±3	±3	±3	±з	±3	±3	
* EXAM													
12-lead ECG	✓										✓		V
Height (screening only) and weight	✓							✓			✓		✓.
Vital signs	✓	✓	*		✓	✓		✓			✓	*	
Physical examination	✓		✓		>	>		\			V	\	
Neurological examination	✓		✓		✓	✓		✓			*	*	
 LAB													
HAV-IgM, HBsAg, HCV Ab, HIV Ab	✓												
Drug and alcohol screen	✓												
Urine pregnancy test (for WOCBP only)			✓			>		>			*		~
Serum pregnancy test (for WOCBP only)	>												
FSH test (for postmenopausal females ≤ age 55 only)	>												
Blood chemistry, hematology (CBC), urinalysis	*		*		*	1		√			V	*	*
Blood samples (plasma) for PK			✓		>	>		>			✓		✓
Blood biomarker sample (plasma)			✓								✓		
Blood biomarker sample (DNA) – collected at any visit			*										
Blood biomarker sample (PAXgene RNA) – optional collection			*								V		
R TREATMENT													
Randomization/drug assignment			✓										
Dispense study drug			✓		✓	✓.		✓					✓
Perform drug reconciliation					>	>		>			✓		✓.

APPENDIX E. PROTOCOL SUMMARY OF CHANGES

Previous Protocol Versions

Protocol	Date
Version 1.0	10 June 2022
Version 2.0	22 September 2022
Version 3.0	13 January 2023
Version 4.0	13 October 2023

The purpose of this version is to correct minor clerical errors for consistency throughout the protocol in addition to the following:

- Protocol Section 5.2 Updated contraception requirements for male.
- Operations Manual (Appendix F), Section 2.1 Deleted footnote in Screening Visit 1
- Operations Manual (Appendix F), Section 1, Updated back-up fax number.
- Operations Manual (Appendix F) Section 4.2 Updated fax number.

APPENDIX F. OPERATIONS MANUAL

1.0 Introduction

This Statistical Analysis Plan (SAP) describes the statistical analyses for ABBV-552 Study M23-515, A Randomized, Double-blind, Placebo-controlled, Dose-finding Study to Evaluate the Safety, Efficacy, Pharmacokinetics, and Pharmacodynamics of ABBV-552 in Participants with Mild Alzheimer's Disease (AD).

Study M23-515 examines the efficacy and safety of ABBV-552 in participants with dementia due to mild AD.

The analyses of pharmacokinetic endpoints and plasma biomarkers will not be covered in this SAP.

The SAP will not be updated in case of administrative changes or amendments to the protocol unless the changes impact the analysis.

Unless noted otherwise, all analyses will be performed using SAS Version 9.4 (SAS Institute Inc., Cary, NC 27513) or later.

This SAP includes changes to analyses described in the protocol. Details are outlined in Section 14.1.

2.0 Study Objectives and Design

2.1 Study Objectives

This is a proof-of-concept, dose-finding study to evaluate the safety, efficacy, pharmacokinetics (PK), and pharmacodynamics (PD) of ABBV-552 once daily for the treatment of dementia due to mild AD.

The primary clinical hypothesis is that at least 1 dose of ABBV-552 (i.e., 1 mg, 5 mg, or 15 mg) is superior to placebo on the primary endpoint in participants with mild AD.

The administration of ABBV-552 once daily will be well tolerated and provide clinical benefit for participants with mild AD.

[figure not shown]
2.2 Study Design Overview

The study will consist of a Screening Period of up to 30 days, a Double-Blind Treatment Period of 12 weeks, and a Safety Follow-up Period of 30 days.

There will be a total of 12 scheduled study visits as shown in Figure 1. The total study duration is approximately 20 weeks.

The schematic of the study is shown in Figure 1.

Figure 1. Study Schematic

2.3 Treatment Assignment and Blinding

Participants will be randomized to placebo, ABBV-552 1 mg QD, ABBV-552 5 mg QD, or ABBV-552 15 mg QD, in a 1:1:1:1 ratio. Randomization will be stratified by whether or not the participant is currently receiving a stable dose of symptomatic treatment for AD at Baseline/Day 1.

2.4 Sample Size Determination

It is assumed that the treatment difference of Alzheimer's Disease Assessment Scale-Cognitive Subscale (ADAS-Cog) 14-item score change from Baseline at Week 12

between each ABBV-552 treatment arm and placebo is 2.85 with a pooled standard deviation of 5.7 (effect size of 0.5) based on data from prior cholinesterase inhibitor and AbbVie studies. The standard deviation of 5.7 was estimated from pooled previous AbbVie symptomatic treatment in mild/moderate AD studies (M10-984, M10-985, M10-822, and M12-033). Assuming a 20% discontinuation rate, 60 participants randomized per group will provide about 80% power to detect the above treatment difference in ADAS-Cog 14 score at the 2-sided 10% significance level. East version 6.5.3 was used for the sample size calculation.

3.0 Endpoints

3.1 Primary Endpoint(s)

The primary endpoint is the change from Baseline in the ADAS-Cog 14 score at Week 12.

3.2 Additional Efficacy Endpoint(s)

Additional efficacy endpoints include:

- Change from Baseline in the Cogstate Computerized Battery at specified timepoints, including Weeks 1, 2, 6, and 12.
- Change from Baseline in the ADAS-Cog 14 score at Week 6.
- Change from Baseline in the Mini-Mental State Examination (MMSE) score at Week 12.
- Change from Baseline in the Clinical Dementia Rating sum of boxes (CDR-SB) score at Week 12.
- Change from Baseline in the Alzheimer's Disease composite score (ADCOMS) at Week 12.
- Change from Baseline in Neuropsychiatric Inventory (NPI) scores at Week 12.

3.3 Safety Endpoint(s)

Safety evaluations include AE monitoring, weight, vital sign measurements, ECG variables, C-SSRS, and clinical laboratory testing (hematology, chemistry, and urinalysis) as measures of safety and tolerability for the entire study duration.

3.4 Other Endpoint(s)

The analysis plan for endpoints related to brain magnetic resonance imaging (MRI) is provided in a separate document and is outside of the scope of this SAP.

4.0 Analysis Sets

The following analysis sets will be used.

The Intent-to-Treat analysis set includes all randomized participants and participants will be grouped according to treatment as randomized.

The modified Intent-to-Treat (mITT) analysis set includes all randomized participants who received at least 1 capsule of study drug and have at least 1 post-baseline ADAS-Cog 14 score. The participants will be grouped according to treatment as randomized. The mITT analysis set will be used for all efficacy analyses, including baseline efficacy summaries.

The safety analysis set consists of all participants who received at least 1 capsule of study drug. The participants will be grouped according to treatment actually received the majority of the time. This will be defined based on the number of days each treatment is received. The safety analysis set will be used for all safety analyses and demographic analyses, unless otherwise noted.

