5.6 Follow-Up After Participant Discontinuation of Study Drug or from Study

To minimize missing data for efficacy and safety assessments, participants who prematurely discontinue study drug treatment should complete the follow-up visit approximately 30 days after study drug discontinuation, unless participants have decided to discontinue the study participation entirely (withdrawal of informed consent).

If a participant prematurely discontinues study participation (withdrawal of informed consent), the procedures outlined for the Premature Discontinuation visit (PD visit) should be completed as soon as possible, preferably within 2 weeks. In addition, if participant is willing, a 30-day follow-up phone call after the last dose of study drug may be completed to ensure all TEAEs/SAEs have been resolved.

In the event a participant withdraws informed consent from the clinical study, biomarker research will continue using the participant's samples, unless the participant explicitly requests analysis of their samples be stopped. When AbbVie is informed the participant has withdrawn and no longer wishes for their biomarker samples to be tested, further sample analysis will not be conducted, and no new biomarker data will be collected for the withdrawn participant. Data generated for biomarker research before participant withdrawal of consent will remain part of the study results.

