7.2 Definition for Analysis Populations

The modified Intent-to-Treat (mITT) analysis set includes all randomized participants who received at least 1 dose of study drug and have at least 1 post-baseline assessment in ADAS-Cog14. The participants will be grouped according to treatment as randomized. The mITT analysis set will be used for all efficacy and demographic analyses.

The safety analysis set consists of all participants who received at least 1 dose of study drug. The participant will be grouped according to treatment actually received the majority of the time. The safety analysis set will be used for all safety analyses.

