The first PROC MI will be performed 100 times using MCMC method for partial imputation of the data with a non-monotone missing pattern. The output dataset will then be used as the input dataset for the next PROC MI. Note that the output dataset already contains 100 copies of the original dataset. With the next invocation of MI procedure, the missing data will be filled in (Steps 1 and 2) for the existing copies. This is achieved with the use of NIMPUTE=1 and a BY _Imputation_ statement. Finally, each of the 100 imputed datasets will be analyzed using an analysis of covariance (ANCOVA) model. The model includes treatment group and randomization stratum as main effects, and baseline ADAS-Cog 14 score as a covariate. The LS mean difference and corresponding SE are estimated from the model comparing each ABBV-552 treatment group with the placebo group. The ANCOVA analysis results from 100 completed datasets are combined for overall estimation and inference using Rubin's rule² to produce a pooled estimate of LS mean difference and its SE. This copy-reference approach sensitivity analysis will be performed on mITT analysis set and safety analysis set.

Two additional sensitivity analyses of the primary endpoint will be provided by alternatively handling the intercurrent events:

ABBV-552
M23-515 – Statistical Analysis Plan
Version 3 – 20 September 2024

- 1. Efficacy data collected after a start, stop or dose change of AD medication during the study will be included in the primary analysis. The same MMRM as specified in the primary analysis will be used.
- Efficacy data collected after participant discontinued study treatment will be excluded in the primary analysis. The same MMRM as specified in the primary analysis will be used.

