9.4.3 Cogstate Brief Battery (CBB) and International Shopping List Test (ISLT)

The CBB consists of the following components: detection test [DET], identification test [IDN], one card learning [OCL], and one back test [ONB]. The ISLT consists of the following: ISLT-Immediate Recall and ISLT-Delayed Recall. Together, the CBB and ISLT are referred to as the Cogstate Computerized Battery (CCB).

The change from baseline for the CCB will be analyzed using an MMRM including treatment group, visit, treatment-by-visit interaction, and the randomization stratum as fixed effects and the baseline score as a covariate. The unstructured covariance structure will be used to estimate the within-participant variance-covariance. Denominator degrees of freedom will be computed using the Kenward-Roger method. The group mean treatment difference between each dose and placebo at Weeks 1, 2, 6, and 12 will be based on contrasts from this model. If the model fails to converge with an unstructured covariance structure, the compound symmetry (CS) covariance structure will be substituted. If the model still fails to converge, data will be analyzed as observed using an ANCOVA model with treatment and the randomization stratum as main effects and the baseline of the measure being analyzed as a covariate.

This will be calculated for the primary outcome measures (e.g., reaction time, accuracy, correct responses) for each component of the CCB as well as the global and domain-specific (attention domain, learning/working memory, and episodic memory) composite scores. The primary outcome measures and calculation details of the composite scores may be found in Appendix C.

Additionally, the effect sizes for the change from baseline for each component of the CCB will be calculated at Weeks 1, 2, 6 and 12.

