14.1 Changes to Planned Analyses in the Protocol

There are currently no changes to the planned analyses in the protocol.

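### Early Cogstate contrasts drop observed Week 1 and 2 data for treated participants who never have a post-baseline ADAS-Cog 14

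*SAP*

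**What the plan says.** SAP 4.0 defines the mITT set as "all randomized participants who received at least 1 capsule of study drug and have at least 1 post-baseline ADAS-Cog 14 score", and states its scope: "The mITT analysis set will be used for all efficacy analyses, including baseline efficacy summaries". Protocol 7.2 has the same condition and a similarly broad scope: "The mITT analysis set will be used for all efficacy and demographic analyses". SAP 9.1 allows another set only where one is noted.

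Cogstate is an additional efficacy endpoint (Protocol 3.3, SAP 3.2). SAP 9.4.3 analyses it with an MMRM and says: "The group mean treatment difference between each dose and placebo at Weeks 1, 2, 6, and 12 will be based on contrasts from this model". That section names no other analysis set, so mITT applies.

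Protocol Appendix D schedules Cogstate after baseline at Weeks 1, 2, 6 and 12/PD and at unscheduled visits. ADAS-Cog 14 is scheduled after baseline only at Weeks 6 and 12/PD and at unscheduled visits.

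One analysis relaxes the ADAS-Cog condition, and it concerns the primary endpoint only (SAP 9.3.3.1): "This copy-reference approach sensitivity analysis will be performed on mITT analysis set and safety analysis set".

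**The concern.** For ADAS-Cog 14 the mITT condition costs nothing: a participant with no post-baseline score has no outcome to contribute. For Cogstate it removes real observations. Whether a Week 1 value counts depends on whether a different scale is measured later, which is a post-randomisation event that may be related to treatment and to performance.

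This conflicts with the missing-data approach in SAP 9.2, which relies on an MMRM without imputation. That approach is justified under missing at random when all observed values enter the likelihood. Here some are removed first.

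The Week 1 and Week 2 Cogstate contrasts are the only efficacy contrasts planned before Week 6, so they are what the study will offer on early effect. The SAP's safety-set analysis of the primary endpoint adds participants whose outcomes must all be imputed. A wider set for Cogstate would add participants with observed outcomes, and no such analysis is planned.

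**Working it through.** **Who is removed.** Setting SAP 4.0 and 9.4.3 beside Appendix D:

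| Treated participant with Week 1 or 2 Cogstate | In mITT? | Early Cogstate used? |
|---|---|---|
| Has ADAS-Cog 14 at Week 6 or Week 12 | Yes | Yes |
| Leaves before Week 6, has ADAS-Cog 14 at a PD or unscheduled visit | Yes | Yes |
| Leaves before Week 6, has no later ADAS-Cog 14 | No | No |

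Only the last row is affected.

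**The plan's own figure.** The documents give no sample size or power for Cogstate. The planning inputs are 60 per arm, 20% discontinuation, a difference of 2.85, SD 5.7 and 2-sided alpha of 0.10 (Protocol 7.8, SAP 2.4). They reproduce the stated primary power: 60 × 0.8 = 48 evaluable; 0.5 / √(2/48) = 2.449; 2.449 − 1.645 = 0.804; power 78.9%, against about 80% stated. The 60 and the 20% are carried forward below.

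**Number at risk.** Neither dropout timing nor PD attendance is given, so these are assumptions: the 20% is loss from assessment, at constant hazard over 12 weeks.

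- Hazard = −ln(0.8)/12 = 0.0186 per week.
- Cumulative loss: Week 1, 1.84%; Week 2, 3.65%; Week 6, 10.56%.
- Week 1 Cogstate observed, then lost before Week 6: 10.56 − 1.84 = 8.71% (from unrounded values); × 60 = 5.2 per arm. As a share of observed Week 1 values: 8.71/98.16 = 8.9%.
- Week 2 likewise: 10.56 − 3.65 = 6.91%; × 60 = 4.1 per arm; 6.91/96.35 = 7.2% of observed Week 2 values.
- Uniform dropout instead: 20% × 5/12 × 60 = 5.0 per arm at Week 1.

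**Size of the shift.** Shift = (share lost × their decrement) on drug − (share lost × their decrement) on placebo, where the decrement is how far those lost fall below those retained, in SD units. The table takes the decrement on drug only.

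| Early leavers with a PD or unscheduled ADAS-Cog 14 | Lost per arm, Week 1 (Week 2) | Share of Week 1 values lost | Shift, 1 SD decrement | Shift, 0.5 SD decrement |
|---|---|---|---|---|
| 0% | 5.2 (4.1) | 8.9% | 0.089 SD | 0.044 SD |
| 50% | 2.6 (2.1) | 4.4% | 0.044 SD | 0.022 SD |
| 80% | 1.0 (0.8) | 1.8% | 0.018 SD | 0.009 SD |
| 100% | 0 | 0% | 0 | 0 |

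Equal share and decrement in both arms give no shift. A decrement on placebo only reverses the sign.

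**Scale.** With 60 × 0.9816 = 58.9 per arm at Week 1, the standard error of a two-arm difference is √(2/58.9) = 0.184 SD. The largest entry is 0.089/0.184 = 0.48 standard errors. The loss of precision is small: with 58.9 − 5.2 = 53.7 retained, the standard error rises by √(58.9/53.7) = 1.05.

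**Simulation check** (59 per arm, unit SD, 8.9% excluded in both arms, 20,000 replicates), all data versus ADAS-Cog-restricted difference: decrement on drug only, −0.089 versus 0.000; on placebo only, +0.090 versus +0.001; in both arms, −0.002 versus −0.002. This confirms the formula. It compares single-visit means and does not fit the planned MMRM.

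**The case against.** The reading of the text is hard to dispute. The case against is about size and proportion.

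- **Weight.** Cogstate is an additional endpoint in a study that calls itself hypothesis-generating and does not control type I error across endpoints (Protocol 7.7, SAP 13.0). The largest shift shown is half a standard error; at 80% PD or unscheduled completion it is about a tenth (0.018/0.184). This stands, and is why the point concerns a supportive result only.
- **The 5.2 per arm is a ceiling under the assumed dropout pattern.** The 20% is a discontinuation rate for sample size and is not stated to be loss from assessment. Participants who withdraw from the study should have a PD visit, which includes ADAS-Cog 14 (Protocol 5.6, Appendix D). One sensitivity analysis in SAP 9.3.3.1 excludes efficacy data collected after study treatment stops, so such data are expected. This also stands; the top row of the table is not a forecast.
- **Existing reporting.** SAP 5.0 tabulates by arm those dosed and those in each analysis population. The difference bounds the number affected but does not show how many had Cogstate data, and it does not restore the data.
- **One common population.** A single mITT keeps all scales on the same participants, and the proposed set is itself conditional on a post-baseline value. That condition discards no observed Cogstate value; the present one does.
- **Sensitivity analysis instead.** Running the wider set only as a sensitivity analysis would be a defensible minimum. It would leave the main Cogstate result on the restricted data.

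**Conclusion.** The concern holds. Followed as written, the plan deletes observed Week 1 and Week 2 Cogstate values for treated participants who never have a post-baseline ADAS-Cog 14, and nothing else in the SAP brings them back.

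Under 60 per arm and 20% loss at constant hazard, the number is 0 to 5.2 per arm at Week 1 and the shift 0 to 0.089 SD for decrements up to 1 SD in one arm. The position in that range depends on PD and unscheduled testing, which the documents do not allow one to predict. The direction is open: a shift in favour of drug requires poor performers on drug to be selectively lost, and the documents do not establish that.

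The primary analysis is not touched. Adverse events, discontinuations and treatment duration use the safety set and are also unaffected. The change is worth making because it is cheap and the data are already collected.

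**What to change.** In SAP 4.0 and 9.4.3, analyse each Cogstate measure in all randomised, treated participants with a baseline and at least one post-baseline value of that measure, grouped as randomised. Report by arm how many of them the ADAS-Cog rule would have excluded. Keep the current mITT for ADAS-Cog 14. MMSE, CDR-SB, NPI and ADCOMS need no change, because their post-baseline visits are ones at which ADAS-Cog 14 is also scheduled.

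Record the departure from Protocol 7.2 in SAP 14.1, which now reads "There are currently no changes to the planned analyses in the protocol". Protocol 7.4 arguably lets the SAP specify another set without such an entry, but 7.2 is unqualified and a line there removes doubt.

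Separately, reconcile Protocol 5.6 with Appendix D. For participants who stop study drug without withdrawing consent, 5.6 names only one visit, saying they "should complete the follow-up visit approximately 30 days after study drug discontinuation", with the stated aim of limiting missing efficacy and safety data. Appendix D schedules neither ADAS-Cog 14 nor Cogstate at that visit. The documents should make clear which assessments apply to these participants.

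The cost of the analysis change is one sentence, one entry in 14.1 and one count by arm. The analysis N will differ slightly between Cogstate and ADAS-Cog 14. No new data are needed.
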